9.5.2.4 Time to progression

Time to progression (IMWG-URC) will be analyzed using the Kaplan-Meier method. Kaplan-Meier survival curves and median time to progression along with 80% CI will be presented.

9.5.2.5 Time to Response (TTR)

Time to response will be descriptively analyzed, summary statistics of the number, percentage will be reported.

9.5.2.6 Duration of Response (DOR)

Duration of response will be conducted based on the subset of subjects having objective response. Kaplan-Meier estimates of median DOR, and their 80% confidence intervals may also be estimated.

9.5.2.7 Anti-AMG224 Antibodies

The incidence and percentage of subjects who develop anti-AMG 224 antibodies (binding) at any time will be tabulated by treatment group. If greater than 10% of subjects have a positive anti-AMG 224 antibody test then summaries of results over time will be provided.

9.6 Safety Analyses

9.6.1 Analyses of Primary Safety Endpoint(s)

Statistical analyses on safety endpoints will be done using subjects from the Safety Analysis Set, which includes subjects that are enrolled and received at least 1 dose of AMG 224.

9.6.1.1 Adverse Events and Disease-related Events

The Medical Dictionary for Regulatory Activities (MedDRA) version version 13.0 or later will be used to code all adverse events to a system organ class and a preferred term.

Treatment-emergent adverse events are events with an onset after the administration of the first dose of investigational product.

The subject incidence of adverse events will be summarized for all treatment-emergent, serious treatment emergent, treatment related, serious treatment related, those leading to withdrawal of investigational product, fatal, and of special interest (if applicable). The identification of adverse events of special interest is a continuous process. Events may be identified and documented as the safety profile of the drug is characterized. The severity of each adverse event will be graded using CTCAE version 4.0 criteria.

Subject incidence of all treatment-emergent, serious, treatment-related, serious treatment related, those leading to withdrawal of investigational product, events of special interest (if applicable) and fatal adverse events will be tabulated by system organ class and preferred term in descending order of frequency. Where appropriate the tables will also be presented by worst grade. The above adverse event tables will not be created if two or fewer subjects experience the adverse event.

Summaries of treatment-emergent and serious AEs occurring in all subjects by preferred term in any cohort will be provided in descending order of frequency.

Details of each adverse event will be listed. Listings and/or narratives of any on-study deaths, serious and significant treatment-emergent adverse events, including early withdrawals due to adverse events, also will be provided should they occur.

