6.2.1.4 Other Stopping Rules During Enrollment

Enrollment will be held at any time during the study if any of the following events occurs:

- DLTs in the first 2 subjects in cohort 1
- Any other study drug-related Grade 5 toxicity

In this case, enrollment and dosing at that particular dose level will be discontinued immediately. Subjects in that dosing cohort will have their treatment dose immediately reduced to the next lower dose level or have study treatment discontinued if the event occurs in Cohort 1 at the starting dose level.

The investigator must discuss the safety findings with all ongoing subjects before continuing AMG 224 to ensure that the subjects understand the risks of continuing AMG 224 therapy.

The sponsor will discuss such cases with the DLRT, Regulatory Authority and the study Investigators as appropriate to decide whether to resume enrollment. IRBs/IEs will be notified by the Investigators of all cases and decisions regarding continued enrollment.

Approved

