10.4.2.2 Adverse Events

Subject incidence of all treatment emergent adverse events will be tabulated by system organ class and preferred term. The number and percentage of subjects reporting adverse events will be evaluated overall and by dose level and will also be tabulated by relationship to study drug.

Tables of fatal adverse events, serious adverse events, adverse events leading to withdrawal from investigational product, and significant treatment emergent adverse events will also be provided.

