9.6.1.3 Laboratory Test Results

9.6.1.3.1 Chemistry, Hematology and Coagulation

Individual chemistry, hematology and coagulation laboratory data will be listed and other selected laboratory parameters of interests may be plotted. The selected laboratory parameters of interest include: platelets, white blood cell, hemoglobin, hematocrit, absolute neutrophil count, lymphocyte, AST, ALT, total bilirubin, and alkaline phosphatase, serum creatinine, PT, PTT, and INR. Values outside the normal laboratory reference ranges will be flagged as high or low on the listings. CTCAE grades will also be highlighted where appropriate. Unscheduled assessments will be incorporated in the laboratory analyses where possible.

The number and percentage of subjects experiencing treatment emergent laboratory toxicities with worst post dose CTCAE grades of ≥ 1 , ≥ 2 , ≥ 3 and 4 will be presented. The direction of the laboratory worsening will be denoted. The summary will be presented for all laboratory parameters for which at least one subject experienced a treatment emergent toxicity with a worst grade ≥ 3 .

Additionally, the number and percentage of subjects experiencing 1, 2, 3 and 4 worsening CTCAE grade shifts from baseline will be presented. The direction of the laboratory worsening will again be denoted.

Shift tables indicating the change between the baseline and the maximum post dose CTCAE grades for an increased value, and the maximum post dose grade for a decreased value will be provided for selected laboratory parameters of interest.

A listing of CTCAE grade 3 or higher laboratory toxicities will be provided. This listing will include all laboratory data for the subject and laboratory parameter of interest in order to provide proper context. A flag will indicate the grade 3 or higher toxicity.

Summaries of the absolute value and/or changes from baseline at each scheduled assessment will be provided for selected laboratory parameters of interest (such as platelets, white blood cell, hemoglobin, hematocrit, absolute neutrophil count, lymphocyte, AST, ALT, total bilirubin, alkaline phosphatase, serum creatinine, PT, PTT, and INR).

A summary of the change from baseline to the post dose maximum, time to post-dose maximum, change from baseline to the post dose minimum, and the time to the post dose minimum may also be provided for selected parameters of interest (such as platelets, white blood cell, hemoglobin, hematocrit, absolute neutrophil count,

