9.8.1 Analyses of Pharmacokinetic or Pharmacokinetic/Pharmacodynamic Endpoints

9.8.1.1 Pharmacokinetic Endpoints

PK parameters will include, but are not limited to maximum observed concentration (C_{max}), minimum observed concentration (C_{min}) and area under the concentration-time curve over the dosing interval [AUC] and if feasible half-life ($t_{1/2}$).

The PK parameters of AMG 224 conjugated antibody, Total anti-BCMA antibody, and DM1 will be estimated using standard noncompartmental methods and summarized by dose level using means, standard deviations, medians, minimums and maximums.

Serum concentrations below the lower limit of quantifications will be set to zero for the estimation of the pharmacokinetic parameters for each subject and for the calculation of the summary statistic for each time point. Actual dosing and sampling time will be used for all calculations. The reasons for excluding any sample from the analyses will be provided.

Individual concentration-time data will be summarized by dose level. AMG 224 conjugated antibody, Total anti-BCMA antibody, and DM1 concentrations at each time point along with PK parameter values may be listed for each subject. Individual concentration-time data will be tabulated and presented graphically. Summary statistics will be computed for each sampling time and parameter as appropriate.

Analysis of the relationship between AMG 224 dose and exposure parameters (AUC and C_{max}) will be conducted and plots of the relationship between AMG 224 dose and exposure parameters along with dose proportionality assessment will be provided.

Analysis of the relationship between AMG 224 conjugated antibody concentrations and change from baseline in QTcF will be conducted and plots of the relationship between AMG 224 conjugated antibody concentrations and change from baseline in QTcF will be

provided. The above analysis will also be conducted for the Total anti-BCMA antibody, and DM1.

Additional analyses to explore relationship between exposure and safety and exposure and efficacy may also be performed.

10. Changes From Protocol-specified Analyses

There are no changes to the protocol-specified analyses.

11. Literature Citations / References

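### Does the SAP's two-subject rule for adverse event tables leave the rarest and gravest events unreported?

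*SAP*

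**What the plan says.** Protocol 10.4.2.2 makes three commitments on adverse events, none with a minimum count:

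- "Subject incidence of all treatment emergent adverse events will be tabulated by system organ class and preferred term".
- Numbers and percentages are "evaluated overall and by dose level and will also be tabulated by relationship to study drug".
- The section further promises "Tables of fatal adverse events, serious adverse events, adverse events leading to withdrawal from investigational product", plus one for events judged significant. No SOC or PT layout is prescribed for these.

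SAP 9.6.1.1 takes this up in several layers. It first promises category-level incidence: "The subject incidence of adverse events will be summarized for all treatment-emergent, serious treatment emergent, treatment related, serious treatment related", and likewise for withdrawals, fatal events and any events of special interest. It then plans SOC/PT tables for the same categories and closes that paragraph with "The above adverse event tables will not be created if two or fewer subjects experience the adverse event". After the rule come preferred-term summaries of treatment-emergent and serious events, a listing of every event, and listings and/or narratives of deaths, serious and significant events and withdrawals due to adverse events. SAP Section 10 states: "There are no changes to the protocol-specified analyses".

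**The concern.** Adverse event incidence is part of the primary endpoint of a first-in-human trial. A rule that suppresses tables when counts are low bears hardest on the categories likely to be both rare and serious: fatal events, withdrawals and serious related events. The protocol sets no such limit, and the SAP says it has changed nothing.

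The sentence is also loosely drafted. It counts subjects, but the singular reference to the event could mean a category or a single preferred term, and no denominator is given. Two programmers could in principle produce different sets of tables.

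Finally, the threshold looks lenient beside others in the plan. Protocol 6.2.1.4 holds enrollment for "Any other study drug-related Grade 5 toxicity", and SAP 9.6.1.3.1 summarises "all laboratory parameters for which at least one subject experienced a treatment emergent toxicity" of grade 3 or worse. If the tables were the only place where rare events appeared, the safety report would be incomplete where it matters most.

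**Working it through.** **1. The plan's own figures.** Protocol 10.2 and SAP 3.2 give the chance of seeing at least one event among 20 subjects, which is 1 − (1 − p)^n:

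- p = 5%: 1 − 0.95^20 = 0.6415 (stated 64%).
- p = 10%: 1 − 0.90^20 = 0.8784 (stated 88%).

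The same binomial model is used below.

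**2. How often the rule would apply.** Count per category over the whole study, n = 60 (Protocol 10.2). Let p be the share of subjects with at least one event in the category, taken as equal across doses. The documents give no category incidences, so the values of p are assumptions. The table is dropped although the category occurred when X = 1 or 2:

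P(X = 1 or 2) = 60·p·(1 − p)^59 + 1770·p²·(1 − p)^58, where 1770 = 60 × 59 / 2.

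At p = 5%: 60 × 0.05 × 0.95^59 + 1770 × 0.0025 × 0.95^58 = 0.1455 + 0.2259 = 0.371.

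| Assumed p | P(X = 0) | P(X = 1 or 2) | P(X = 1 or 2, given X ≥ 1) |
|---|---|---|---|
| 1% | 0.547 | 0.430 | 0.951 |
| 2% | 0.298 | 0.584 | 0.831 |
| 5% | 0.046 | 0.371 | 0.389 |
| 10% | 0.002 | 0.051 | 0.051 |
| 20% | 0.000 | 0.0002 | 0.0002 |

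A category seen in 5% of subjects or fewer may well lose its SOC/PT table. One seen in 20% or more will not. The table of all treatment-emergent events, the only one for which the protocol fixes the SOC/PT layout, would be lost only if at most two subjects in the whole study had any adverse event.

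**3. What still reports the events when a table is dropped.**

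| Category | Protocol 10.4.2.2 asks for | Still reported under SAP 9.6.1.1 |
|---|---|---|
| Fatal | A table | Category-level incidence; serious-event PT summary, because Protocol 9.1.2 makes fatal a seriousness criterion; listing and/or narrative |
| Serious | A table | Category-level incidence; serious-event PT summary; listing and/or narrative |
| Withdrawal | A table | Category-level incidence; treatment-emergent PT summary; listing and/or narrative |
| Related | Tabulation by relationship | Category-level incidence; treatment-emergent PT summary, not split by relationship; event listing |
| Serious related | No separate table | Category-level incidence; serious-event PT summary; event listing |

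The loss is the SOC grouping and the category-specific display for one or two subjects, at most 2/60 = 3.3% of the study.

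**4. Dose decisions.** The outputs for the dose level review meetings in SAP Appendix A include a listing of reported adverse events and none of these tables. DLTs have their own listing and incidence summary in SAP 9.6.1.2, without a threshold.

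**The case for a change.** The best case for a change is that the protocol promises tables, the SAP withholds some of them without declaring it, and a listing is not a tabulated incidence. The preferred-term summaries cover treatment-emergent and serious events only, so no preferred-term display is specific to fatal, withdrawal or related events once the table is gone. The undefined scope also matters on paper: two subjects are 3.3% of 60, 10% of the 20 in Part 2 and 33% of a cohort of 6. Deleting the sentence would cost only a few short tables.

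Part of this stands. The sentence is imprecise, and a note in SAP Section 10 would have been tidier. The rest carries little weight:

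- For fatal, serious and withdrawal events the protocol prescribes no layout, and the category-level incidence summary arguably meets its request.
- The 10% and 33% figures need a count per preferred term within a part or cohort. That fits the text poorly, because a table is created for a category, not for each preferred term.
- For one or two people, a listing or narrative says more than an SOC/PT frequency table.
- The other thresholds serve other purposes. The enrollment hold is a conduct rule, supported by serious event reporting within 24 hours (Protocol 9.2.1.2), not by end-of-study tables. The laboratory condition is a display trigger for a different output, as is the 10% trigger for antibody summaries in SAP 9.5.2.7. Such triggers need not agree.

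**Conclusion.** No change follows, because there is nothing to gain. On the natural reading (count per category, over the whole study), the rule removes an SOC/PT layout for a category with one or two affected subjects and leaves those subjects counted, listed and, for the grave categories, covered by a listing or narrative. No data are lost, no estimate changes and no dose decision uses the tables. Stating the level and scope of the count would only write down what analysts can settle sensibly when they specify the tables.

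This rests on three readings. The category-level incidence summary, which stands in an earlier paragraph of SAP 9.6.1.1, is outside the rule. The preferred-term summaries, which come after it, are also outside, and their clumsy wording means that they cover every subject. The count is per category. If instead it were per preferred term, the loss would extend to the relationship split of preferred terms seen in one or two subjects. Those events would still appear in the treatment-emergent preferred-term summary and the listing. The probabilities above depend on assumed incidences and show only how often the rule might apply.

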9.6.1.2 Dose Limiting Toxicities

The analysis of the probability of DLT will be based on the DLT Evaluable Analysis Set. A listing and summary of the subject incidence of DLT will be provided.

A final estimate of the MTD will be estimated from the TPI Bayesian model utilizing all DLT-evaluable subjects. A sensitivity analysis may also be performed where DLTs

occurring outside of the specified time interval are included. A listing of DLTs occurring outside of the specified time interval will be produced to aid in determining if the sensitivity analysis should be conducted.

The planned doses for dose exploration cohort are 30, [REDACTED] of AMG 224. It will use a standard 3+3 design to guide dose escalation decisions and to make a preliminary estimate of the MTD. Dose level decision rules are specified in [Table 1](#).

In the dose expansion cohort, up to 20 subjects would be treated at the preliminary MTD. After 5 subjects (combining Group A and B) have completed 28 days on study, there will be a safety review by the DLRT. A TPI Bayesian model utilizing all current DLT evaluable subjects will be fit to evaluate appropriateness of preliminary MTD from dose exploration phase. As more subjects are treated, there may be a higher than expected incidence of DLTs or a higher than expected tolerance of treatment. If these scenarios (either with higher toxicity or tolerance) occur during expansion cohort the additional data will be used to refine the estimate of MTD established during the dose escalation phase. (Iasonos A and O'Quigley J, 2013).

A minimally informative prior distribution will be used for the model parameters (Neuenschwander, 2008). The MTD target probability interval is (0.20, 0.35) and TPIs of (0.35, 0.60) and (0.60, 1.00) are defined as excessive and unacceptable, respectively. The model's predicted MTD dose is the dose with the highest probability of the target TPI, but with a less than 0.25 probability of an excessive or unacceptable TPI.

The TPI design seeks to identify a dose most likely to have a DLT rate in the target TPI, but with overdose control that limits the possibility that the dose has an excessive or unacceptable DLT rate ([Babb et al, 1998](#)). The probability of a DLT at dose level d_i is assumed to follow a Bernoulli distribution with probability p_i where the logit of p_i increases linearly with the log of the standardized dose in the following 2-parameter logistic model:

$$\log [p_i / (1-p_i)] = \text{logit}(p_i) = \log[a] + \exp(\log[b]) \log (d_i / d_{\max})$$

where a and b are random variables and d_{\max} is the maximum planned dose.

The probability of each TPI and of a DLT will be summarized by dose along with the estimated dose-toxicity curve. A final estimate of the MTD will be estimated from the TPI Bayesian model utilizing all DLT-evaluable subjects. Please refer to [Appendix A](#) (Toxicity Probability Interval (TPI) Bayesian Design section) for more details on the TPI model.

9.6.1.3 Laboratory Test Results

9.6.1.3.1 Chemistry, Hematology and Coagulation

Individual chemistry, hematology and coagulation laboratory data will be listed and other selected laboratory parameters of interests may be plotted. The selected laboratory parameters of interest include: platelets, white blood cell, hemoglobin, hematocrit, absolute neutrophil count, lymphocyte, AST, ALT, total bilirubin, and alkaline phosphatase, serum creatinine, PT, PTT, and INR. Values outside the normal laboratory reference ranges will be flagged as high or low on the listings. CTCAE grades will also be highlighted where appropriate. Unscheduled assessments will be incorporated in the laboratory analyses where possible.

The number and percentage of subjects experiencing treatment emergent laboratory toxicities with worst post dose CTCAE grades of ≥ 1 , ≥ 2 , ≥ 3 and 4 will be presented. The direction of the laboratory worsening will be denoted. The summary will be presented for all laboratory parameters for which at least one subject experienced a treatment emergent toxicity with a worst grade ≥ 3 .

Additionally, the number and percentage of subjects experiencing 1, 2, 3 and 4 worsening CTCAE grade shifts from baseline will be presented. The direction of the laboratory worsening will again be denoted.

Shift tables indicating the change between the baseline and the maximum post dose CTCAE grades for an increased value, and the maximum post dose grade for a decreased value will be provided for selected laboratory parameters of interest.

A listing of CTCAE grade 3 or higher laboratory toxicities will be provided. This listing will include all laboratory data for the subject and laboratory parameter of interest in order to provide proper context. A flag will indicate the grade 3 or higher toxicity.

Summaries of the absolute value and/or changes from baseline at each scheduled assessment will be provided for selected laboratory parameters of interest (such as platelets, white blood cell, hemoglobin, hematocrit, absolute neutrophil count, lymphocyte, AST, ALT, total bilirubin, alkaline phosphatase, serum creatinine, PT, PTT, and INR).

A summary of the change from baseline to the post dose maximum, time to post-dose maximum, change from baseline to the post dose minimum, and the time to the post dose minimum may also be provided for selected parameters of interest (such as platelets, white blood cell, hemoglobin, hematocrit, absolute neutrophil count,

lymphocyte, AST, ALT, total bilirubin, alkaline phosphatase, serum creatinine, PT, PTT, and INR).

Potential Hy's law cases will be listed and may also be summarized per cohort and overall. A listing of AST, ALT, Total Bilirubin values at each time point will be produced for the subjects suspected of fulfilling the criteria for Hy's law.

9.6.1.3.2 Urinalysis

Individual urinalysis data will be listed.

9.6.1.4 Vital Signs

Vital signs data (systolic / diastolic blood pressure, heart rate, respiratory rate, and temperature) will be listed and reviewed for each subject. Depending on the size and scope of changes, summaries of vital signs data over time and/or changes from baseline over time may be provided.

9.6.1.5 Electrocardiogram

All on-study electrocardiogram (ECG) data will be listed. All on-study electrocardiogram (ECG) data will be listed and QTcF will be plotted.

Where multiple 12-lead ECG measurements are taken at the same assessment (they are planned to be recorded in triplicate 30 seconds apart) the mean value will be calculated and used in the analysis. For baseline ECG, three triplicate ECGs to be collected ≥ 30 minutes apart, with each ECG in triplicate approximately 30 seconds apart (3 set collected predose on day 1 with total of 9 ECGs). Mean value will be calculated and used in the analysis. The mean of the values within a triplicate should be calculated before taking the mean of the triplicate averages.

For pre and post dose ECG measurements, unscheduled ECG measurements taken up to 5 minutes after the last assessment of a triplicate will be included in the average for a time point. Where an ECG is missing within a triplicate, all available data will be averaged for that time point.

Summaries over time and/or changes from baseline over time will be provided for all 12-lead ECG parameters.

Subjects will be categorized into the following groups per their maximum change from baseline in QTcF. Unscheduled assessments will be included in the determination of the maximum change.

- ≤ 30 msec
- > 30 – 60 msec
- > 60 msec

The number and percentage of subjects in each group will be summarized.

Subjects will also be categorized into the following groups per their maximum post baseline QTcF. Unscheduled assessments will be included in the determination of the maximum post baseline value.

- ≤ 450 msec
- > 450 – 480 msec
- > 480 – 500 msec
- > 500 msec

The number of subjects in each group will be summarized for each dosing group.

In addition, the relationship between PK concentration of AMG 224 and change from baseline in QTcF may be explored graphically.

Analysis of the relationship between AMG 224 serum concentrations and change from baseline in QTcF will be conducted and plots of the relationship between AMG 224 serum concentrations and change from baseline in QTcF will be provided.

In addition, the relationship between drug concentration (AMG 224 conjugated antibody, Total anti-BCMA antibody, and DM-1) and QTcF will be explored graphically.

